#### W4: Intermediary assessment: repeat of W2

W8: Intermediary assessment: repeat of W2/4

W16: Intermediary assessment: repeat of W2/4/8

**W26:** Follow-up assessment: All outcome measures listed at W0 and intermediary assessments are repeated, with the exception of some sociodemographic information gathered at baseline only (specified above).

Additionally, participants will be asked for feedback regarding study conduct and their experiences (including satisfaction regarding amount/detail of information received, clarity of information, extent of support during the study, logistics, suggestions for improvements to their experience) and they will be asked whether they would consider continuing or restarting lithium supplementation in the future (self-management, outside of research).

#### **10.2.** Laboratory Tests

Collection of blood samples will be identical between intermediary assessments (2 x serum tube). Blood samples will be collected by a trained clinical nurse following local SOPs. Collection and processing will be conducted according to the Clinical Research Facility at King's College Hospital SOPs. Samples will be immediately processed and transferred to Synnovis' local laboratories as per collaboration agreements in accordance with Human Tissue Act procedures. 2 serum samples will be analysed for lithium levels and biomarkers on a regular basis (within one week of transfer) according to standard lithium laboratory procedures. Sample tubes will not contain any identifiable information and could be linked with participant data only by using the collection pack label, unique to each study participant and corresponding to their participant ID. After samples have been analysed, any surplus biological material will be disposed of in accordance with the Human Tissue Act 2004 Code of Practice.

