# 6. Study Objectives and Design

## 6.1. Study Objectives

This research aims to elucidate LiOr's plausibility, at a known safe dose, over an extended period in a preliminary study. This is a feasibility study comprising the preliminary work required prior to formal trials examining commercially available LiOr supplementation for DMF. No specific hypotheses are therefore proposed. In this open label study, people who constitute a target population for LiOR will be invited to take commercially available LiOr for up to six months to establish its plausibility as a putative intervention for trials. The specific objectives are to investigate up to six months of open-label 20mg daily LiOr to identify its within-subjects effects on the following as co-primary outcomes:

1. The potential to examine bioavailability of LiOr (i.e. whether lithium is present at detectable levels in the serum using a standard laboratory lithium test), assessing lithium levels in serum.

2. The acceptability of 20mg daily LiOr over 6 months (assessed by self-report adherence and discontinuation rates) to inform a future study design.

3. Description of any positive and/or negative experiences of 20mg daily LiOr over 6 months (assessed via participant-report) to inform a future study design.

4. The feasibility of the protocol including intervention delivery and assessment visits (including assessments mentioned above, plus putative primary (mood) and secondary (functioning, cognition) outcome measures and assessment of potential confounders). Overall feasibility will be assessed via missing data and study withdrawal rates.

An exploratory analysis of change will be undertaken as secondary objectives for measures over time to inform a future definitive study design:

1. LiOR's biological effects, through assessment of key candidate blood-based biomarkers, namely neuroprotective growth factors (BDNF, VEGF) and inflammatory cytokines (IL-6, TNFa, IL-1b, IL-8, CRP) between week 0 and week 26.

2. LiOr's effects on mood, through assessing changes in mood ratings between week 0 and week 26.

3. LiOr's effects on cognition and functioning, through assessing changes in cognitive and psychosocial function between week 0 and week 26.

These aims will be met via within-subjects comparisons for each timepoint relative to baseline (weeks 2, 4, 8, 16, 26).

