#### 6.2. Study Design

A single site, one arm unblinded open label study investigating the effects of LiOr supplementation (20mg, once per day) for up to six months. We will recruit 40 people for this feasibility study.

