## 9.7. Expected Duration of Study

The total study duration for a given participant will be 26 weeks. Week 0 will comprise the baseline assessment and LiOR initiation will occur as soon as feasible after this. Intermediary assessments will be conducted at week 2, week 4, week 8 and week 16, followed by the final follow-up assessment and discontinuation of LiOR at week 26. The beginning of the study overall will be Week 0 (baseline assessment) of the 1st participant, estimated October 2024, and the end of the study will be one month after the last week of the 40th participant's follow-up assessment, estimated to be in August 2025, to allow for sample analysis.

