1. LiOR's biological effects, through assessment of key candidate blood-based biomarkers, namely neuroprotective growth factors (BDNF, VEGF) and inflammatory cytokines (IL-6, TNFa, IL-1b, IL-8, CRP) throughout the study. This will be examined using a repeated-measures ANOVA according to the intention-to-treat principle, with a sensitivity analysis to examine only adherent participants.

2. LiOr's effects on mood, through assessing changes in mood ratings (M3VAS, ISS, IDS, YMRS) throughout the study. These will be examined using a repeated-measures ANOVA according to the intention-to-treat principle, with a sensitivity analysis to examine only adherent participants.

3. LiOr's effects on cognition and psychosocial function, through assessing changes in THINC-IT and FAST scores respectively, throughout the study. These will be examined using a repeated-measures ANOVA according to the intention-to-treat principle, with a sensitivity analysis to examine only adherent participants.

Ancillary exploratory analyses will examine other wellbeing outcomes (e.g., EQ5D), service use, and a potential impact of bipolar features on outcomes during the study. Additional exploratory analyses using the data collected may be conducted.

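### Biomarkers are assayed within a week of each draw and surplus serum is discarded, so under the planned analysis assay drift is read as change from week 0 to week 26

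*Protocol*

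**What the plan says.** Section 10.2 sends serum to the laboratory straight after each draw: "Samples will be immediately processed and transferred to Synnovis' local laboratories". It then sets one timetable for both uses of the blood: "2 serum samples will be analysed for lithium levels and biomarkers on a regular basis (within one week of transfer"). Nothing is kept afterwards: "After samples have been analysed, any surplus biological material will be disposed of in accordance with the Human Tissue Act 2004 Code of Practice".

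The same blood test is taken at weeks 0, 2, 4, 8, 16 and 26 (sections 6.3 and 10.1). Secondary objective 1 in section 6.1 is change in BDNF, VEGF and "inflammatory cytokines (IL-6, TNFa, IL-1b, IL-8, CRP) between week 0 and week 26". For the analysis, section 12.2 states: "This will be examined using a repeated-measures ANOVA according to the intention-to-treat principle, with a sensitivity analysis to examine only adherent participants". Section 6.2 describes "A single site, one arm unblinded open label study". Section 9.7 puts the first baseline in October 2024 and the end of the study one month after the last follow-up, "estimated to be in August 2025, to allow for sample analysis".

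The protocol mentions no stored aliquots, no bridging or quality-control samples across runs, and no run, lot or date term.

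**The concern.** Prompt assay suits lithium, because section 11.1 acts on lithium levels as results arrive. The protocol gives no reason for treating the exploratory biomarkers the same way. For them, the schedule places each person's first and last samples in runs about six months apart. If calibration drifts, or the reagent lot changes in between, every participant's value moves in the same direction. No control group exists to cancel that movement, and no serum remains for a repeat assay.

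At stake is the biomarker change estimate that section 6.1 intends for designing a later study. A shift in the assay could look like a biological effect of the supplement, or could hide one.

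**Working it through.** The protocol gives no figure for assay drift, so there is none to reproduce. The check has four steps.

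**1. Do the assay windows overlap?** Inputs from section 9.7: first week 0 in October 2024; end of study in August 2025, one month after the last week 26.

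- Last week 26: 1 to 31 August 2025 minus 30 days = 2 July to 1 August 2025.
- Last week 0: minus 182 days = 1 to 31 January 2025. Its assay is due by 7 February 2025 at the latest.
- First week 26: 1 October 2024 plus 182 days = 1 April 2025 at the earliest.

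The latest week 0 assay (7 February) and the earliest week 26 draw (1 April) are at least 53 days apart. On these dates no week 0 sample can share a run with any week 26 sample. If recruitment ran late, the windows might meet across participants, but each person's own two samples would still be 26 weeks apart.

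**2. Smooth drift.** Calendar date = participant's entry date + visit week. With participant and visit effects in the model, a linear date term adds nothing: 40 participant effects + 5 visit effects = 45 columns of rank 45, and adding date makes 46 columns, still of rank 45. Linear drift is exactly aliased with visit. A drift of 0.01 residual SD per week gives an apparent week 26 change of 26 × 0.01 = 0.26 SD.

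**3. Lot steps.** Assumed: 40 participants entering evenly over the longest recruitment period (17.4 weeks), equally spaced lots, and each new lot 0.25 residual SD higher than the last. The bias is the difference in mean lot number between week 26 and week 0, times 0.25.

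| Lots | Week 0 samples per lot | Week 26 samples per lot | Bias, visit-only ANOVA | Variance ratio if lot is modelled |
|---|---|---|---|---|
| 2 | 40, 0 | 0, 40 | 0.25 SD | 2.6 |
| 3 | 33, 7, 0 | 0, 7, 33 | 0.41 SD | 4.4 |
| 4 | 25, 15, 0, 0 | 0, 0, 15, 25 | 0.56 SD | 7.5 |

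With three lots, for example, (66/40) × 0.25 = 0.41. Modelling lot is possible because staggered entry and the intermediate visits link the lots. The last column is what that costs, relative to a base standard error of √(2/40) = 0.224 residual SD.

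**4. False-positive rate.** Assumed: one common shift between all week 0 and all week 26 samples, no true change, and a paired two-sided 5% test on the log scale. With d = ln(1 + shift) / (SD/√n), the rate is 1 − Φ(1.96 − d) + Φ(−1.96 − d). For n = 40:

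| Shift | SD of log change | d | False-positive rate |
|---|---|---|---|
| 10% | 0.6 | 0.0953/0.0949 = 1.00 | 17% |
| 10% | 0.4 | 0.0953/0.0632 = 1.51 | 33% |
| 20% | 0.6 | 0.1823/0.0949 = 1.92 | 48% |
| 20% | 0.4 | 0.1823/0.0632 = 2.88 | 82% |

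With 20 completers the ranges are 11 to 19% and 27 to 53%.

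**The case against.** **The text may be meant for lithium only.** The sentence in section 10.2 ends by referring to standard lithium procedures, and section 9.7 holds a month for sample analysis, which suggests that some assays come later. But the sentence names biomarkers explicitly and fixes one week for both. The month in section 9.7 does not override it.

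**Lot effects can be modelled.** This stands in part. A reader might infer that drift can never be separated from true change. That is strictly so only for smooth drift, or under the visit-only ANOVA described. Recorded lot steps are estimable, with the loss of precision shown above, and an analysis plan that is not shown could include them.

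**The size is assumed.** This stands. The shift sizes, the SDs and any change of lot come from outside the protocol. The calculation puts one full shift, in one direction, between every week 0 and every week 26 sample. Laboratory quality control, which is not described, may keep drift small.

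**The outcome is minor.** This stands as to severity. Section 6.1 proposes no hypotheses, section 12.1 does not aim at statistical significance, and no co-primary outcome uses these markers. A single arm also cannot attribute change to the supplement, because regression to the mean, season and changes in other treatment remain. Assay drift is nevertheless an avoidable bias added to those limits.

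**Batching has its own confounding.** This stands. Week 0 serum would be stored about six months longer than week 26 serum, so storage time follows visit.

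**Conclusion.** The concern holds for the plan as written: prompt biomarker assay, disposal of surplus, separate calendar windows, one arm and a visit-only analysis together turn any common assay shift into apparent within-person change. This rests on the estimated dates in section 9.7 and on a literal reading of section 10.2.

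How large the bias would be is unknown. The 17 to 33% (10% shift) and 48 to 82% (20% shift) rates are worst-case illustrations and not predictions. A reader might infer that the biomarker results will be wrong or that the main conclusions are at risk; the protocol supports neither. It gives no evidence that drift will occur, and the outcome is secondary and exploratory. The change should be made, and before sampling, because discarded serum cannot be recovered.

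**What to change.** In section 10.2, separate the two uses of the blood.

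- Keep the lithium assay within one week of transfer.
- Freeze a serum aliquot at each visit. Assay BDNF, VEGF and the cytokines with all of a participant's visits in the same run and reagent lot, in random order. A common run or lot offset then cancels from the within-person change.
- Delay disposal until these assays are done, and amend the retention text and the laboratory agreement to match.
- Record storage time and confirm that the analytes are stable over it.

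If storage is not possible, run common bridging or quality-control samples across runs, and record and model run and lot.

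Cost: freezer space for about 40 × 6 = 240 aliquots, the amended wording, and later biomarker results. The month in section 9.7 is already set aside for sample analysis, and the May 2025 interim in section 12.2 covers primary analyses only, so it does not need these results. Participants undergo no extra procedure.

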## 11. Assessment of Safety

#### 11.1. Assessment of Therapy Safety

Safety is not an outcome of this study, as the supplement has been evidenced to be safe (having been available and used without supervision, in the community, for decades). However, the welfare of our participants is paramount, and we will closely monitor information obtained from participants to ensure their safety. Specifically, this includes monitoring of lithium levels and wellbeing measures (as soon as each information are available to the research team). Monitoring and proposed actions comprise:

- a. If any abnormalities are noted from clinical blood tests, participants and their GPs will be informed within one working day by study researchers. NB these are likely to be incidental, not associated with the intervention, given evidence to date of safety.
- b. If any lithium levels exceed 0.6mmol/L, the dosing regime will be lowered from 20mg to 10mg as maximum dose as soon as practicable. This would be highly unexpected, given that the typical dose of lithium carbonate required to achieve therapeutic levels (0.6-0.8mmol/L) is 600-800 (approximately 6-8 times the elemental equivalent in LiOR 20mg).
- c. If >50% participants (at any point in time) report a desire to reduce from 20mg, the dosing regimen will be lowered from 20mg to 10mg as soon as practicable.
- d. If any wellbeing concerns arise in general, participants will be contacted within one working day by a study researcher for a wellbeing discussion and to provide support (i.e., study-related actions, signposting e.g., to support or healthcare services).

#### 11.2. Specification, Timing and Recording of Safety Parameters

The study researcher will be responsible for checking with the participant verbally that there are no current negative effects and will record any injuries, notable events or other phenomena that might be of concern. These will be treated as any adverse event in any trial (see section 11.3). Any concerns will be communicated to the Lead Investigator (RS) and the medical expert ([name]).

#### 11.3. Procedures for Recording and Reporting Adverse Events

Any adverse events will be recorded by a researcher at each visit asking participants if they have had any troubles and record these systematically. Even though LiOR is not a medicinal product, the standard definitions provided by The Medicines for Human Use (Clinical Trials) Regulations 2004 and Amended Regulations 2006 with regards to adverse events will be used, as follows:

Adverse Event (AE): Any untoward medical occurrence in a subject to whom an intervention has been administered including occurrences which are not necessarily caused by or related to that intervention.

Adverse Reaction (AR): Any untoward and unintended response in a subject to an intervention which is related to the intervention administration to that subject.

Unexpected Adverse Reaction (UAR): An adverse reaction the nature and severity of which is not consistent with the information about the intervention in question.

Serious Adverse Event (SAE), Serious Adverse Reaction (SAR) or Suspected Unexpected Serious Adverse Reaction (SUSAR): Any adverse event, adverse reaction or unexpected adverse reaction, respectively, that: results in death; is life-threatening; required hospitalisation or prolongation of existing hospitalisation; results in persistent or significant disability or incapacity; consists of a congenital anomaly or birth defect.

Important Medical Events (IME): Events that may not be immediately life-threatening or result in death or hospitalisation but may jeopardise the patient or may require an intervention to prevent one of the other outcomes listed in the definition above should also be considered serious.

Any AEs (excepting those specified in this protocol as not requiring reporting; see below section 11.4) that occur throughout the duration of the study will be recorded in the participant case report form. Investigators will assess whether the AE may be related to study participation and will also assess the severity of the event. Documented AEs reported after a participant signs the consent form will be included in the primary study report.

All AEs classified as ARs and UARs will be recorded and immediately addressed with the Chief Investigator (certainly no later than 24 hours), as well as be considered in Steering Group Meetings. All SAEs and SARs will be reported immediately (certainly no later than 24 hours) by the Chief Investigator to the Sponsor and the R&D office using a SAE report form. In accordance with the Health Research Authority procedures, only SUSARs will be reported by the Chief Investigator to the Research Ethics Committee for review (sent within seven days of the reaction for fatal or life-threatening events and 15 days of the reaction for not fatal or life-threatening events).

Although we do not anticipate any SARs or SUSARs, participants presenting any such reactions will be withdrawn from LiOR and, if not already done by the participant, these reactions will be brought to the attention of their named healthcare professional. Non-serious ARs may also warrant a referral back to the named healthcare professional, but withdrawal from the study will depend on risk assessment, circumstances and participant's wishes.

All SAEs that have not resolved by the end of the study, or that have not resolved upon discontinuation of the subject's participation in the study, will be followed until: the event resolves, the event stabilises, the event returns to baseline (if a baseline value is available), the event can be attributed to agents other than the study participation or to factors unrelated to the study, when it becomes unlikely that any additional information can be obtained. All follow-up information for SAEs that have not resolved by the end of the study or by the time of participant withdrawal will be reported to the Sponsor.

#### 11.4. Adverse events that do not require reporting

No SAEs are expected in this study. Therefore, any SAEs will be reported as will ARs, UARs, SARs or SUSARs or IMEs. AEs that do not meet the above criteria but require intervention (e.g., safety concerns communicated to healthcare professional or incidence of acute episode requiring changes to treatment regime) will be reported. Other AEs do not require reporting (e.g., mild distress disclosed by participants where no further action is required or unrelated to the study/LiOR).

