## 12.1. Sample Size

As an initial feasibility study, a sample size calculation is not warranted. However, a sample of 40 participants permits estimation of a 50% dropout rate to within a 95% confidence interval of +/-15%.[Research Design Service. NIHR. Available at: https://www.rds-london.nihr.ac.uk/resources/justify-sample-size-for-a-feasibility-study/]. The existence of six repeated measures and focus on within-subjects change/variability will help boost power to observe effects without aiming to determine statistical significance of effects with any precision.

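### Non-serious adverse events judged unrelated and needing no intervention are exempted from the case report form, contrary to the opening of Section 11.3, so that part of the AE count rests on unblinded attribution

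*Protocol*

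**What the plan says.** Four statements in Protocol Section 11 bear on what is recorded.

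- Section 11.3, first sentence: "Any adverse events will be recorded by a researcher at each visit asking participants if they have had any troubles and record these systematically".
- Section 11.3, AE definition: it covers any untoward medical occurrence, "including occurrences which are not necessarily caused by or related to that intervention".
- Section 11.3, CRF rule: "Any AEs (excepting those specified in this protocol as not requiring reporting; see below section 11.4"), when they occur during the study, go into the participant's CRF. Investigators then assess possible relatedness and severity, and documented AEs arising after consent go into the primary study report.
- Section 11.4: serious events, reactions of every class and important medical events are reported. So are other AEs that require intervention. It closes: "Other AEs do not require reporting (e.g., mild distress disclosed by participants where no further action is required or unrelated to the study/LiOR").

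Two other sections set the context. Section 9.5 states that nobody is blinded. Section 19 states that source data are collected on paper CRFs and entered from there into the database.

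**The concern.** Section 11.4 reads as a rule about what is passed on to the sponsor or the ethics committee. The cross-reference in Section 11.3 makes it a rule about what is written down. These are different functions: exempting a minor event from onward reporting is ordinary, whereas exempting it from the CRF removes it from the data.

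Two things follow. First, Section 11.3 contradicts itself: its opening sentence and its AE definition bring unrelated events in, and its CRF rule takes some of them out. Staff at the visit cannot follow both. Second, the order of judgement is reversed. Relatedness should be a field completed for a recorded event, but here it becomes a condition of being recorded.

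At stake is the AE count promised for the primary report. If a minor complaint recurs across participants and each instance is called unrelated when it arises, the AE record would show no cluster. Nobody could later revisit the attributions, because the protocol names no other place where the events are kept. This matters more for a product that Section 5 says has not been subject to clinical trials.

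**Working it through.** **The plan's own figures.** The protocol gives no figure for adverse events. Its only precision statement concerns dropout: "a sample of 40 participants permits estimation of a 50% dropout rate to within a 95% confidence interval of +/-15" percentage points. Check: 1.96 × √(0.5 × 0.5 / 40) = 0.155, or 15.5 points, which agrees to rounding. Only n = 40 is carried forward (Section 6.2: "We will recruit 40 people for this feasibility study").

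**Step 1. Apply the rule to every type of event.** Under Sections 11.3 and 11.4, an AE reaches the CRF if it is serious (or an important medical event), or judged related (hence a reaction), or requires intervention.

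| Serious | Judged related | Needs intervention | In CRF |
|---|---|---|---|
| yes | yes | yes | yes |
| yes | yes | no | yes |
| yes | no | yes | yes |
| yes | no | no | yes |
| no | yes | yes | yes |
| no | yes | no | yes |
| no | no | yes | yes |
| no | no | no | **no** |

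Seven of the eight combinations are kept. The last row and the row for a related event needing no intervention differ only in the relatedness judgement. Within non-serious events needing no intervention, attribution is therefore the sole gate.

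**Step 2. Compare with the opening of Section 11.3.** Under the first sentence and the AE definition, all eight rows should be recorded. The conflict is exactly the last row.

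**Step 3. Trace the omitted row.** It is not in the CRF (Section 11.3). The paper CRF is the source record (Section 19). Only documented AEs enter the primary report (Section 11.3). No other store for AEs is named.

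**Step 4. Illustrate the scale.** These rates are assumptions and are not in the protocol. Let p be the proportion of participants with one non-serious AE needing no intervention, and u the share of these judged unrelated. The proportion counted is q = p(1 − u), the expected count is 40q, and, with participants independent, the chance that none is counted is (1 − q)^40.

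| p | u | Expected count, 40q | Chance none counted |
|---|---|---|---|
| 10% | 0 | 4 | 0.90^40 = 1.5% |
| 10% | 25% | 3 | 0.925^40 = 4.4% |
| 10% | 50% | 2 | 0.95^40 = 12.9% |
| 10% | 75% | 1 | 0.975^40 = 36.3% |
| 25% | 0 | 10 | below 0.1% |
| 25% | 25% | 7.5 | below 0.1% |
| 25% | 50% | 5 | 0.5% |
| 25% | 75% | 2.5 | 7.6% |

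The fall in the expected count simply restates u. The last column adds that, for less common complaints in a sample of 40, the filter can remove a signal altogether.

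**The case against.** The case for leaving the text alone has substance, and it rules out several stronger readings.

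- **Breadth.** From the word joining the two conditions in the Section 11.4 example, a reader might infer that every unrelated event, and every event needing no action, is dropped. The preceding sentences of Section 11.4 do not allow that. A related event needing no action is an adverse reaction and is kept, as is an unrelated event that needs intervention. The example is loosely worded, but it does not override the rule.
- **Co-primary objective 3.** A reader might infer that the negative-effects objective is biased. It is not measured from the AE log. It uses the participant-reported LiSERS at weeks 2, 4, 8, 16 and 26, with no attribution step. This objection stands. However, LiSERS is a lithium side-effect scale described as a continuous score for negative experiences (Section 12.2), so it does not replace a count of AEs.
- **Staff primed to dismiss events.** Section 11.1 calls abnormalities probably incidental, but only those found in clinical blood tests, and it has them passed to participants and GPs. It says nothing about mild symptoms.
- **Section 11.2.** Its statement "These will be treated as any adverse event in any trial" refers to events that might be of concern. It does not promise that all AEs are recorded, so the contradiction lies within Section 11.3 alone.
- **No comparison to distort.** With one arm, attribution cannot differ between arms. The test in Section 11.3 is also inclusive, since it asks only whether the event may be related. Both points stand and limit the harm, but a single-arm AE count can still be too low.
- **Proportionality.** Section 11.1 says safety is not an outcome and Section 14 calls the study low risk. That argues for a modest priority. It does not remove the contradiction, because Section 11.3 itself commits to AEs in the primary report.

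**Conclusion.** The point holds in a limited form. Through its cross-reference to Section 11.4, Section 11.3 excludes from the CRF those AEs that are non-serious, not judged related and not requiring intervention. This contradicts its own first sentence and its AE definition. The gap is one of eight combinations. Within non-serious events needing no intervention, unblinded attribution alone determines what is counted.

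The protocol supports no estimate of how many events would be lost, and the figures in the working are illustrations only. The statement that omitted events cannot be re-judged assumes that the CRF is the only AE record, which is what Section 19 implies. This is an inexpensive improvement to the AE record and does not undermine the co-primary outcomes.

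**What to change.** In Section 11.3, delete the exception so that every AE arising after consent is entered in the CRF, with severity and relatedness as fields. Retitle and reword Section 11.4 so that it governs only onward or expedited reporting, and replace its example with one that states the conditions jointly. State that the primary report will give all recorded AEs, overall and by relatedness.

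Researchers already ask about troubles at each visit, so the cost is a few extra AE lines per participant. Expedited reporting does not change.
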